5.4.3.2 Additional Secondary Endpoints Analyses

- Syncope. The occurrence of this event will be analysed in the primary efficacy population using a Cox proportional hazards model as was performed in the primary efficacy analysis (NI, using an NI margin of 1.20). Patients who had not experienced syncope at the time of data base lock will be censored at the last known-alive date.
- Clinical and healthcare resource utilisation data collected in this study including ICD implantation, all hospitalisations, treatment of AEs, and AdreView™ administration will be used in an economic evaluation of study outcomes for relevant geographies. The clinical data may be summarised and compared between the AdreView™ and SoC groups. The healthcare resource utilization data will not be analysed due to early termination.
- A composite of the rate of hospitalisation and death related to major complications of device implantation (i.e., need for thoracotomy, pericardiocentesis, or vascular surgery) and a composite of the rate of complications of long-term device therapy (i.e., infection not leading to hospitalisation, lead and/or generator removal/replacement, inappropriate shocks, explantation). The occurrence of these events will be analysed using a Cox proportional hazards model as described in the primary efficacy analysis. These data will be analysed with a superiority analysis (HR of AdreView™ vs SoC < 1.0), using a 2-sided alpha value of 0.05. Kaplan-Meier plot will be presented by method of treatment guidance. Patients who had not experienced any of the events at the time of data base lock will be censored at the last known-alive date.
- The rate of ICD implantation and ICD explantation will be summarized for each study arm. In addition, the reasons of ICD implantation and ICD explantation will also be summarized. The odds ratio of the rate of ICD implantation and ICD explantation will be compared between the AdreView™ and SoC groups using the CMH test stratified by country.

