7.4 Withdrawal and Termination Criteria

7.4.1 Patient Withdrawal

There are no formal withdrawal criteria for this study. During the conduct of the study, the Sponsor may review the safety data for trends and signals that would indicate the need for withdrawal of a patient.

In accordance with the Declaration of Helsinki, each patient is free to withdraw from the study at any time. Investigator(s) also have the right to withdraw patients from the study in the event of illness, AEs, or other reasons concerning the health or well-being of the patient, or in the case of lack of co-operation.

Should a patient decide to withdraw after administration of AdreView™, or should the investigator(s) decide to withdraw the patient, all efforts will be made to complete and report the observations up to the time of withdrawal as thoroughly as possible. A complete final evaluation at the time of the patient's withdrawal should be made and an explanation given of why the patient is withdrawing or being withdrawn from the study. As this is an intention to treat analysis, all patients should be followed for the primary endpoint of all-cause mortality if at all possible. ICD crossover or having a secondary endpoint is not a reason to withdraw from the study.

The reason for withdrawal must be noted in the electronic Case Report Form (eCRF). If the reason for withdrawal is a serious adverse event (SAE), monitoring will continue until the outcome is evident. The specific event or test result(s) must be recorded in the eCRF. The reason for withdrawal must be noted in the eCRF. If the reason for withdrawal is a clinical AE, monitoring will continue until the outcome is evident. The specific event or test result(s) must be recorded in the eCRF. Patients withdrawing prior to completing the study may be replaced.

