- i ICD interrogation does not need to be performed on the same day as the corresponding follow-up visit. ICD interrogation may be done remotely within ± 5 days of the corresponding follow-up visit.
- j AdreView™-emergent AEs are defined as any AE which occurs within 24 hours after administration of AdreView™, and in addition any AE which occurs more than 24 hours after administration of AdreView™ for which a causal relationship is assumed by the investigator.
- k Patients will be enrolled and followed up until sufficient endpoints have accrued (247 primary endpoint events). All patients will then attend an end-of-study visit within 1 month.

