9.6 End of Study Visit

This will be an event-driven study. Patients will be enrolled and followed up until sufficient endpoints have accrued (247 primary endpoint events). All patients will then attend an end-of-study visit within 1 month.

If a patient discontinues prematurely, he/she will attend an end of study visit at that time. As this is an intention-to-treat analysis, all patients should be followed for the primary endpoint of all-cause mortality if at all possible.

The following parameters will be collected:

- Medical history (with identification of study end-points)
- Concomitant medications
- Vital signs (blood pressure, heart rate, respiratory rate, and pulse oximetry)
- A brief physical examination will be performed.
- AEs, SAEs and AdreView™-emergent AEs
- All data related to primary and secondary endpoints
- ICD interrogation (for those patients with an ICD); may be performed remotely within ±5 days of follow-up visit.

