5.4.3 Secondary Efficacy Analyses

5.4.3.1 Key Secondary Endpoints Analyses

- A composite of the proportion of patients with hospitalisation or death related to major complications of device implantation (i.e., need for thoracotomy, pericardiocentesis, or vascular surgery) and a composite rate of complications of long-term device therapy (i.e., infection not leading to hospitalisation, lead and/or generator removal/replacement, inappropriate shocks, explantation). This endpoint will be analysed for superiority (odds ratio of AdreView™ vs SoC < 1.0). These proportions will be compared between the patients with H/M ≥ 1.60 in the AdreView™ group and the patients with H/M ≥ 1.60 in the SoC group, using the Cochran-Mantel-Haenszel (CMH) test stratified by country, using a 2-sided alpha value of 0.05.
- Cardiac death. The occurrence of this event will be analysed using a Cox proportional hazards model as described in the primary efficacy analysis (NI, using an NI margin of 1.20). Kaplan-Meier plot will be presented by method of treatment guidance. Patients who were alive or who had died from other than cardiovascular causes at the time of data base lock will be censored at the last known-alive date.
- Rate of hospitalisation for cardiovascular cause. The odds ratio of this rate will be compared between the AdreView™ and SoC groups using the CMH test stratified by country (NI, using an NI margin of 1.20).

- Rate of all-cause hospitalisation. The odds ratio of this rate will be compared between the AdreView™ and SoC groups using the CMH test stratified by country, (NI, using an NI margin of 1.20).
- A composite of the occurrence of resuscitated life-threatening ventricular tachycardia, unstable ventricular tachy-arrhythmias, SCD and resuscitated cardiac arrest. The first occurrence of these events will be analysed using a Cox proportional hazards model as described in the primary efficacy analysis (NI, using an NI margin of 1.20). Kaplan-Meier plot will be presented by the study arm. Patients who had not experienced any of the events at the time of data base lock will be censored at the last known-alive date.

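### Syncope and two composites are censored at the date used for mortality, so time after early discontinuation can be counted as event-free without having been assessed

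*SAP*

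**What the plan says.** SAP 5.4.2 censors survivors at the last known-alive date for all-cause mortality. Section 5.4.3.2 uses the same date for syncope: "Patients who had not experienced syncope at the time of data base lock will be censored at the last known-alive date". For the arrhythmia composite, which ends in "unstable ventricular tachy-arrhythmias, SCD and resuscitated cardiac arrest", section 5.4.3.1 says: "Patients who had not experienced any of the events at the time of data base lock will be censored at the last known-alive date". Section 5.4.3.2 repeats that sentence for the AdreView versus SoC composite of "hospitalisation and death related to major complications of device implantation" and long-term device complications. All three are analysed by the Cox model of the primary analysis.

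On early discontinuation, Protocol 9.6 says: "If a patient discontinues prematurely, he/she will attend an end of study visit at that time". Protocol 7.4.1 has other observations completed to the point of withdrawal, and then "all patients should be followed for the primary endpoint of all-cause mortality if at all possible". There is one exception: "If the reason for withdrawal is a clinical AE, monitoring will continue until the outcome is evident" (the same is said for an SAE). Neither document sets a separate censoring date for non-fatal events.

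**The concern.** A censoring date should be the last date at which the event would have been recorded had it occurred. For death, being known alive meets that test. For syncope, a resuscitated arrhythmia or an inappropriate shock it does not.

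Take a patient who leaves at month 12 and is confirmed alive at month 30. The SAP credits 30 months free of syncope, of which 18 were not assessed. This has two consequences:
- Rates and cumulative incidence are too low in any arm that contains such time.
- If the arms contain different amounts, the hazard ratio moves towards favouring the arm with more unassessed time.

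The composites are affected less than syncope. Their fatal components (SCD, device-related death) can still be learned from mortality follow-up, but the non-fatal components cannot. Each composite therefore mixes two observation windows.

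**Working it through.** The plan gives no figure on this point, so there is nothing to reproduce. The size depends on quantities that the documents do not report.

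**Assumptions (none from the documents).** A share w of an arm discontinues at uniform times over 3 years. A share c of the resulting unassessed time is covered by later vital status. The event hazard is constant and equal in the two arms (true HR 1.00). The SAP planned an average of 2.75 to 3 years of follow-up, but the study was stopped early and actual follow-up is not given.

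**Rate factor.** Assessed share of person-time = 1 − w/2. Time counted by the SAP rule = 1 − w/2 + c·w/2. The observed rate is the true rate times (1 − w/2)/(1 − w/2 + c·w/2).

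| c | AdreView, w = 20% | SoC, w = 10% | HR shown |
|---|---|---|---|
| 1 | 0.90/1.000 = 0.900 | 0.95/1.0000 = 0.950 | 0.947 |
| 0.5 | 0.90/0.950 = 0.947 | 0.95/0.9750 = 0.974 | 0.972 |
| 0.25 | 0.90/0.925 = 0.973 | 0.95/0.9625 = 0.987 | 0.986 |
| 0 | 1.000 | 1.000 | 1.000 |

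With the imbalance reversed (10% versus 20%) the HRs are 1.056, 1.028 and 1.014. At 10% versus 5% with c = 1 the HR is 0.950/0.975 = 0.974. Equal loss gives 1.00 at any c.

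**Cumulative incidence under equal loss, c = 1.** Risk shown = 1 − (1 − p)^(1 − w/2). For a true 3-year risk p = 10%:
- w = 10%: 1 − 0.9^0.95 = 9.5%.
- w = 20%: 1 − 0.9^0.90 = 9.0%.

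**Composites and the choice of remedy.** A simulation used 4,000,000 patients per arm over 3 years, with 10% non-fatal events, 3% SCD, 9% other death, equal hazards and c = 1.

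| Quantity | SAP rule | All components stopped at last assessment | Later deaths counted, survivors cut at last assessment |
|---|---|---|---|
| Syncope HR, 20% vs 10% | 0.948 | 1.000 | – |
| Composite HR, 20% vs 10% | 0.961 | 1.002 | 1.013 |
| Composite HR, 10% vs 20% | 1.042 | 1.001 | 0.989 |
| Composite rate, 20% in both arms | ×0.92 | ×1.00 | ×1.02 |

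Stopping at the last assessment removes the distortion. It also leaves out SCDs that occur after the last assessment in patients with no earlier counted event: 4.7% of SCDs at w = 10% and 9.5% at w = 20%. The mixed rule in the last column overstates the rate.

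**The case against.** **Later vital status may be scarce.** Mortality follow-up after discontinuation is qualified as where possible, and Protocol Table 1 schedules no contact after the end-of-study visit. Where there is no later contact, the last known-alive date is that visit and the rule does no harm. This stands: 0.95 is the extreme for 20% versus 10%, and the c = 0.25 and 0.5 rows belong beside it.

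**Unequal loss is not shown.** The documents give no withdrawal rate, overall or by arm. Protocol 7.4.1 says that ICD crossover or a secondary endpoint is not a reason to withdraw. This also stands. Open allocation (SAP 2.5) makes an imbalance possible, but its size and direction are unknown.

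**Other data may still be collected.** Protocol 9.4 says generally that events and safety data are gathered throughout the study. This carries less weight: 7.4.1 ends other observations at withdrawal, and 7.4.1 and 9.6 name only mortality afterwards. A general sentence does not make a vital-status check an assessment of syncope.

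**Stronger readings that the documents do not support.**
- A reader might infer that the rule would produce false non-inferiority. With a true HR of 1.20, 10% SoC versus 20% AdreView withdrawal and every withdrawn patient later known alive, a Cox simulation gave about 7% false non-inferiority against the nominal 2.5%. That needs assumed rates and full capture, and SAP 5.4.4 gives these tests no confirmatory role.
- A reader might also infer that the hospitalisation odds ratios are biased because they ignore time at risk. Under concurrent 1:1 randomisation an ever/never comparison is valid, and early stopping shortens both arms alike. The only imbalance derivable from the documents is assumed mortality, 11.34% versus 13.33% at 3 years. With exponential survival, the person-time ratio is [0.1134/−ln(0.8866)]/[0.1333/−ln(0.8667)] = 1.011. At an assumed 40% hospitalisation risk this gives an OR of 1.01 to 1.02. A time-to-first-event analysis would be a preference.

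**Conclusion.** The point holds for three analyses: syncope, the arrhythmia composite and the all-patient device composite. As written, the rule counts unassessed time as event-free for discontinued patients who are later confirmed alive. Patients followed to the end-of-study visit, and those with no later contact, are not affected.

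Reported rates and curves are then understated even under equal loss. With 20% discontinuing in both arms and all of their time covered, a true 10% risk is shown at most about 1 point too low. The HR is distorted only by unequal unassessed time: about 0.95 to 0.99 for syncope at 20% versus 10%, about 1.01 to 1.06 in the reverse case, and somewhat less for a composite with SCD. All of these figures rest on assumed discontinuation and capture rates.

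All-cause mortality and cardiac death are correctly dated. The device composite in patients with H/M ≥1.60 is a CMH comparison of proportions with no censoring date, so the point does not reach it. Because secondary results are for reference only, this is an optional improvement. The estimates will still be reported, though, and the absence of formal testing does not correct them.

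**What to change.** Amend SAP 5.4.3.1 and 5.4.3.2 as follows.

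1. **Syncope.** Censor at the last visit or contact at which syncope was assessed, or at death if the patient dies while still in follow-up. Do not use ICD interrogation as this date. Only patients with a device have it, and low-risk AdreView patients initially have none, so the date could differ by arm. Also, "ICD interrogation may be done remotely within ± 5 days of the corresponding follow-up visit", and the documents do not say that interrogation assesses syncope.
2. **Arrhythmia composite and all-patient device composite.** As the main version, censor all components at the last assessment. Show the present last known-alive version as a sensitivity analysis, so that SCDs and device-related deaths learned later are kept. Do not count later deaths while cutting survivors at the last assessment.
3. **Reporting.** Give, per arm, the person-time between the last assessment and the last known-alive date. If it is small and balanced, the reader can see that the choice does not matter.
4. **Unchanged.** All-cause mortality, cardiac death, the H/M ≥1.60 device composite and the hospitalisation odds ratios stay as they are. All secondary results remain for reference only.

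The cost is SAP wording, one extra derived date per patient and a rerun of the existing Cox program. The downside is that two versions of each composite must be read together.

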9.3 Post-Randomisation Procedures

All female patients (unless pre-menarchal, surgically sterile or post-menopausal) will undergo a serum or urine pregnancy test on the day of and prior to AdreView™ administration. AdreView™ dosing will only commence if the result is negative.

AdreView™ will be administered to all patients.

The first AdreView™ administration should be performed in the 15 (+7) days post-randomisation. Starting at 3 hours 50 minutes after administration of AdreView™, patients will undergo a 10-minute acquisition of anterior planar images of the thorax, and whenever possible these will be followed by a SPECT acquisition. Details of the acquisition and transmission of images to the Sponsor are provided in the study Imaging Manual.

Only those patients allocated to the AdreView™ arm will have the results of the scan (H/M ratio calculated on an anterior planar image obtained at 3 hours and 50 minutes for 10 minutes, and with regions placed following the standard quantification method according to the Imaging Manual) available to make a decision on the need for implantation of an ICD. In patients allocated to the SoC group, the investigator will remain blinded to the results of the AdreView™ images and any information derived from them in order not to influence the decision to implant or not implant an ICD.

Patients in the AdreView™ arm who are deemed at high-risk for all-cause and cardiovascular mortality (H/M ratio <1.6 as defined in Section 6.1) will undergo ICD device implantation. ICD implantation should be performed within 45 days of randomisation. Patients deemed to be at low risk (H/M ratio ≥ 1.6 as per Section 6.1) will continue to receive guideline-directed optimal medical therapy but will not undergo ICD implantation. In the low risk group, a second AdreView™ scan will be performed at 2 years following the first scan, or in case of early withdrawal, prior to this withdrawal being effective.

Patients randomly allocated to the SoC group will undergo ICD implantation and will be managed and followed up in accordance with internationally accepted HF guidelines. ICD implantation should be performed within 45 days of allocation to the SoC group. The results of the AdreView™ scan will remain blinded to the investigator to avoid any influence regarding patient management. AEs, SAEs and AdreView™-emergent AEs will be recorded.

All data related to primary and secondary endpoints will be collected.

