9.4 Follow-Up

After randomisation, all patients will be followed up according to medical practice. However a follow-up visit will occur at least every 6 months. Additionally, all patients in whom an ICD is implanted will also have a follow-up visit 3 months after the procedure has taken place.

Patients will be followed up for the specified time and events and safety data will be collected throughout the entire study.

For those patients whose clinical status worsens during the follow-up period, the investigator will decide on the necessity for ICD implantation based entirely on the risk/benefit to the patient and patient eligibility for ICD implantation.

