9.5 Second AdreView™ Administration

Patients in the low-risk AdreView™ group will undergo a second AdreView™ scan (planar and possibly SPECT) 2 years post-randomisation for purposes of re-stratification. All female patients will undergo a serum or urine pregnancy test unless pre-menarchal, surgically sterile or post-menopausal prior to this scan. Should the H/M ratio fall under 1.6 and the patient is willing and eligible for ICD implantation, he/she should receive an ICD. Should the patient withdraw prior to study termination the second AdreView™ scan will be offered prior to said withdrawal being effective.

- AEs, SAEs and AdreView™-emergent AEs will be recorded
- All data related to primary and secondary endpoints will be collected
- Injection site monitoring will be performed before and after injection (with findings recorded pre-administration, 15 minutes post-administration, and at discharge from the imaging suite)

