Patients with $25\% \leq \text{LVEF} \leq 35\%$, and meeting all other inclusion criteria and not meeting any of the exclusion criteria, were enrolled and randomly assigned to the AdreView™ group or the SoC group in a ratio of 1:1. All patients were to be scheduled for an AdreView™ scan. The results of the AdreView™ scan in the SoC group were to remain blinded to the investigator to avoid any influence in the decision of implanting an ICD. The binary assessment of risk (i.e., either high or low) was made for the AdreView™ patient group based on the H/M measurement made by the site personnel on the AdreView™ planar image (i.e. H/M < 1.6 was high risk vs H/M ≥ 1.6 was low risk). Only the high/low risk classification was made known to the investigator and as such was used to determine ICD implantation in the AdreView group per protocol. Patients with AdreView™ H/M ratio < 1.6 (high 1- and 2-year mortality risk) were to undergo ICD device implantation. Patients with AdreView™ H/M ratio ≥ 1.6 (low 1- and 2-year mortality risk) continued to receive guideline-directed optimal medical therapy according to clinical standard practice and did not undergo ICD implantation initially, but could receive an ICD at a later stage should they develop further symptoms and after assessment by the investigator. Patients in this latter group were to undergo a second AdreView™ scan (planar and possibly SPECT) 2 years post-randomisation for purposes of re-stratification. Patients allocated to the SoC group were to undergo ICD implantation and to be managed and followed up in accordance with internationally accepted HF guidelines.

Patients were to attend follow-up visits at the rate determined by the investigator, in accordance with their clinical standard practice. However, a follow-up visit had to take place at least every 6 months (an extra follow-up visit was to be performed at 3 months after ICD implantation). All patients were also to attend an end-of-study visit.

Table 1 Study Schedule of Events

Variable	Screening / Enrolment Visit *	Randomisation	Post-Randomisation Procedures	Follow-Up Visit at 3 months post-ICD implantation (for patients with ICD implanted) (± 15 days)	Follow-Up Visit at 6 months post-randomisation and then at least every 6 months (± 15 days)	Second AdreView™ Administration at 2 years (± 30 days) post-randomisation (low-risk cohort only)	End-of-Study Visit ^k
Informed consent ^a	X						
Inclusion/exclusion criteria	X						

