6 SPECIAL STATISTICAL TOPICS

This study was discontinued prematurely by the sponsor. Due to the early termination of the study, the following objectives for the study will not be performed and will be evaluated in the future if needed.

- The healthcare resource utilization data including ICD implantation, all hospitalizations, treatment of AEs, and AdreView™ administration
- Statistical relationship between AdreView™ global and/or regional distribution quantified on Single Photon Emission Computed Tomography (SPECT) images with the same clinical outcomes as with planar H/M ratio

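### The between-arm comparison of ICD implantation ignores follow-up time, so early termination lowers AdreView ICD use to the extent that low-risk patients missed the 2-year re-scan and would have converted

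*SAP*

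**What the plan says.** The last bullet of SAP 5.4.3.2 summarises the rates of ICD implantation and explantation by arm, adds that "the reasons of ICD implantation and ICD explantation will also be summarized", and then says that "The odds ratio of the rate of ICD implantation and ICD explantation will be compared between the AdreView™ and SoC groups" by a CMH test stratified by country. A CMH odds ratio needs one yes/no outcome per patient, and no time is named, so the natural reading is any ICD during whatever follow-up the patient had. The time-to-event endpoints in the same section use Cox models with censoring at the last known-alive date.

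Timing differs by group:

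- **SoC.** Protocol 9.3: "ICD implantation should be performed within 45 days of allocation to the SoC group". The 45-day limit also applies to high-risk AdreView patients.
- **Low-risk AdreView.** No ICD after the first scan. SAP 2.2: "Patients in this latter group were to undergo a second AdreView™ scan (planar and possibly SPECT) 2 years post-randomisation for purposes of re-stratification". Protocol 9.5 adds: "Should the H/M ratio fall under 1.6 and the patient is willing and eligible for ICD implantation, he/she should receive an ICD".
- **Any patient who worsens.** Protocol 9.4: "the investigator will decide on the necessity for ICD implantation based entirely on the risk/benefit to the patient", together with the patient's eligibility for an ICD. SAP 2.2 likewise allows a later ICD in low-risk patients who develop further symptoms.

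SAP 6 records that "This study was discontinued prematurely by the sponsor". Neither document gives the stop date, the number randomised or the follow-up achieved.

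**The concern.** Most ICDs in the SoC arm and in the high-risk part of the AdreView arm should be placed in the first weeks, so they are seen even in patients with short follow-up. The scheduled second chance of an ICD exists in one subgroup of one arm, and it comes late. Stopping the trial before patients reach 2 years removes implants from that subgroup and has no counterpart in SoC. An odds ratio without a time horizon mixes patients observed before and after the re-scan, and its value depends on how accrual lay relative to the stop date.

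ICD use is how the two strategies differ in practice. A reader of the final report would take this comparison as the effect of AdreView guidance on ICD use. It would describe the strategy partly or wholly before its own re-stratification step, and nothing in the planned output would show how far.

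**Working it through.** **1. Low-risk share.** The plan states no size or power for the ICD comparison. The related figure is the 24% low-risk share in Protocol 12.10 and SAP 2.3. From the sample-size table (21% with H/M ≥1.6 in the lower LVEF band, 25% in the upper, ratio 1:4): 0.2 × 21% + 0.8 × 25% = 4.2% + 20.0% = 24.2%. This reproduces the plan's 24%.

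**2. Would the planned trial have covered the re-scan?** The sample-size inputs give a minimum follow-up of 48 − 18 = 30 months. Protocol 6.3 (6 years in total, 32-month recruitment) gives 72 − 32 = 40 months. On either basis every survivor still in the study passes 24 months, so f is about 1. The mean observation time of 2.75 to 3 years (33 to 36 months) in the same section sits awkwardly with this. With uniform 32-month recruitment and deaths ignored, it implies a minimum of 33 − 16 = 17 to 36 − 16 = 20 months. On any of these bases, stopping earlier than planned can only lower f.

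**3. Is the re-scan provided at termination?** Protocol 8.1.1, 8.3 and 9.5 offer it early to patients who withdraw. The end-of-study visit in Protocol 9.6 includes no scan, and no section provides one when the sponsor stops the study.

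**4. What f might be.** The stop date is unknown. Assume uniform 32-month accrual and ignore deaths and withdrawals. For a stop at month T, from 32 on, the share with 24 months of follow-up is (T − 24)/32, up to a maximum of 1. This gives 12/32 = 38% at month 36, 24/32 = 75% at month 48 and 100% from month 56. At month 24 it is 0%.

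**5. Shortfall in AdreView ICD use.** Assume full adherence (all high-risk AdreView patients implanted). Let c be the share of low-risk patients who receive an ICD because of the re-scan. Observed AdreView ICD use is 75.8 + 24.2 × c × f percent, and with every re-scan done it is 75.8 + 24.2 × c. The shortfall is 24.2 × c × (1 − f) points:

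| c (assumed) | f = 1 | f = 0.75 | f = 0.5 | f = 0 |
|---|---|---|---|---|
| 10% | 0 | 0.6 | 1.2 | 2.4 |
| 20% | 0 | 1.2 | 2.4 | 4.8 |
| 30% | 0 | 1.8 | 3.6 | 7.3 |
| 50% | 0 | 3.0 | 6.1 | 12.1 |

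ICDs placed earlier for worsening shrink the pool that can convert, and so shrink these figures.

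**6. Effect on the contrast.**
- *SoC 100% implanted.* The reduction is 24.2 × (1 − c × f) points. At c = 20% it reads 24.2 at f = 0, 21.8 at f = 0.5 and 19.4 at f = 1. At f = 0 it is overstated by 24.2/19.4 − 1 = 25%. At c = 10% the overstatement at f = 0 is 11%.
- *SoC at 15%, the existing-practice figure in the sample-size model.* AdreView uses more ICDs: 75.8% against 15% at f = 0, an excess of 60.8 points. At c = 20% and f = 1 it is 80.6% against 15%, an excess of 65.6. Truncation then understates an excess by the same 4.8 points.
- *Odds ratio.* With an assumed 95% uptake in SoC and in high-risk AdreView patients and c = 20%, AdreView ICD use is 0.95 × 75.8 = 72.0% at f = 0 and 72.0 + 4.8 = 76.8% at f = 1. The odds ratios are 0.135 and 0.175.

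**The case against.** The strongest reply is that no bias has been shown. It needs some low-risk patients to have missed the re-scan and some of those to have been due to convert, and the documents quantify neither. Conversion also depends on willingness and eligibility, and Protocol 8.3 says such a patient could receive an ICD where 9.5 says should; those two passages need reconciling. This stands, and it is why the shortfall is given as a conditional range that includes nil.

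Nor is the re-scan the only route to a later ICD. Worsening can lead to one earlier, in either arm. That also stands. What differs between arms is the scheduled re-decision.

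The direction of the contrast depends on SoC uptake. Protocol 6.1 and 9.3 say SoC patients will be implanted, Table 1 footnote h refers to each site's standard of care, and the sample-size model uses 15%. This limits any statement about a saving, but AdreView ICD use is too low in either case.

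Finally, SAP 5.4.4 makes all secondary results reference only, and per-arm rates and reasons for implantation are tabulated. That lowers the stakes. Reasons without dates or numbers at risk still do not show how many patients were observed past the re-scan.

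**Conclusion.** The point holds in conditional form. The planned comparison takes no account of follow-up, and early termination can remove scheduled implants only from low-risk AdreView patients. AdreView ICD use is therefore too low, relative to the planned strategy, by 24.2 × c × (1 − f) points: nil if all reached 2 years, 4.8 points at c = 20% and f = 0. This rests on the plan's 24.2% low-risk share, on assumed full adherence, and on c and f, which are assumptions.

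A reader might infer more, and the documents do not support it:

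- *The ICD saving is overstated.* This needs f < 1, c > 0 and high SoC uptake. None is documented as achieved.
- *Low-risk patients can get an ICD only at the re-scan.* Protocol 9.4 and SAP 2.2 say otherwise.
- *The odds ratio will make a modest reduction look very large.* That would require a reader to take it for a risk ratio and overlook the per-arm rates reported with it. The scale is a secondary matter.
- *Low-risk patients who die before the re-scan are wrongly counted as spared an ICD.* They did not receive one, and a competing-risk analysis counts them the same way. Their assumed 36-month mortality is 4.68% to 9.72%.

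**What to change.** In SAP 5.4.3.2:

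1. Make the main comparison the cumulative incidence of first ICD by arm, with death as a competing event and censoring at end of follow-up.
2. Read it at 45 days, just before the re-scan window (2 years ± 30 days) and, if enough patients remain at risk, after it. Give percentage-point differences with 95% confidence intervals.
3. Report how many low-risk AdreView patients reached the re-scan time, were re-scanned, and received an ICD afterwards. These counts replace the assumed c and f.
4. If the CMH odds ratio is kept, label it *within observed follow-up*.

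As a minor clarification, reconcile SAP 6, which lists ICD implantation among resource data not to be analysed, with 5.4.3.2, which compares it. The split between clinical and resource-use data in 5.4.3.2 suggests that only the economic use was withdrawn, but the text should say so.

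The cost is SAP wording and one table from dates already collected. The downside is that the later time points may be imprecise, or not estimable if few patients passed 2 years. In that case the report should say that the data describe the strategy before re-stratification.
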